8.0 Subject Numbers and Statistical Plan

8.1 Number of Subjects

Participants will be enrolled in the study until a total of 45 are randomized. We anticipate that we will need to enroll up to 70 participants in order to randomize 45.

8.2 Sample size determination

Previous studies have shown the effects of NRT on cessation in sample sizes that are comparable to (e.g., [name], et al., 1992; Rose, et al., 1998; Rose, et al., 2006) the one proposed here (n=15 per treatment arm). Based upon such work, we are confident that we will have sufficient power to achieve the aim of the proposed research.

8.3 Statistical methods

Paired sample t-tests (or nonparametric Wilcoxon Rank-Sum tests) will be used to examine changes in the outcome measures (CPD, CO, subjective measures, BP, HR) from baseline.

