1.0 Objectives

1.1 Study Objectives

The objective of this study is to determine whether treatment with random nicotine delivery via nicotine film both before and after the quit date will facilitate cessation relative to treatment with steady state delivery or placebo. We hypothesize that smoking cessation will be greater in subjects assigned to a random nicotine delivery regimen (as compared to those assigned to a steady state or placebo regimen). The nicotine film product is not part of the standard of care and is not available in non-investigational settings in the United States.

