1.2 Primary Study Endpoints

The primary endpoints for the study include the percent reduction in the number of cigarettes smoked and the accompanying percent reduction in exhaled carbon monoxide (CO) levels.

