3.0 Inclusion and Exclusion Criteria

3.1 Inclusion Criteria

1. Aged 18-55
2. Smoke ≥ 10 cigarettes/day for at least the past 12 months
3. Exhaled CO measurement ≥ 6 ppm at baseline visit
4. Interested in completely ceasing cigarette consumption and using a nicotine film product as directed
5. Willing to attend regular visits over a 6-week period (not planning to move, not planning extended vacation, no planned surgeries)
6. Able to read and write in English
7. Able to understand and consent to study procedures

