7.0 Study Design and Procedures

7.1 Study Design

This is a randomized, double-blind, placebo-controlled, parallel-group study that will occur in three phases over 7 weeks.

Time & Events Table								
	Baseline	Pre-Cessation			Cessation			
Study Week Number	-1	0	1	2	3	4	5	6
Study Visit Number	1	2	Ph #1	3	Ph #2	4	Ph #3	5
Study Day Number	-7	0	7	14	21	28	35	42
MEASURES								
Screener 3	X							
Concomitant medications	X	X	X	X	X	X	X	X
Medical history	X							

NIDA Quick Screen	X						
Cigarette details	X						
Adverse events		X	X	X	X	X	X
Daily cigarette/film diary collection		X	X	X	X	X	X
Demographics	X						
Tobacco Use History	X						
Environmental Tobacco Smoke Questionnaire		X		X		X	X
Cigarette Evaluation Scale		X	X	X	X	X	X
Nicotine dependence		X		X		X	X
Minnesota Withdrawal Scale		X		X		X	X
Questionnaire Smoking Urge		X		X		X	X
Perceived Stress		X		X		X	X
Confidence to quit		X		X		X	X
Study product side effects			X	X	X	X	X
Study product evaluation			X	X	X	X	X
Likelihood of Use Scale				X		X	X
Dose Awareness							X
BIOMEASURES							
Height		X					
Weight		X		X		X	X
Waist/Hip ratio		X					X
Exhaled CO	X	X		X		X	X
Blood pressure & pulse	X	X		X		X	X
Pregnancy test	X			X		X	

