7.4.2 Treatment Regimen

Nicotine films will be administered orally. They are used by placing a film on the tongue, closing the mouth, and pressing the tongue gently to the roof of the mouth. The film will dissolve in the mouth within 5 minutes. Three doses of nicotine film will be used in this study: 0, 2, and 4 mg.

Participants will be randomized to one of three possible treatment regimens:

- 1) **Random nicotine delivery** (a combination of four 0 mg and 4 mg films daily not to exceed three non-consecutive 4 mg films in one day and to maintain an average of 8mg of nicotine per day through 7 days for 6 weeks total)
 - a) Possible weekly random delivery dosing scenarios to maintain an 8 mg/day average through 7 days:
 - a. One 4mg day, five 8mg days, and one 12mg day in any order
 - b. Two 4mg days, three 8mg days, and two 12mg days in any order

Possible Daily Sequences for Random Delivery		
4mg/day	8mg/day	12mg/day
4000	4400	4404
0400	4040	4044
0040	4004	
0004	0440	
	0404	
	0044	

- 2) **Steady state nicotine delivery** (2, 2, 2, 2 mg films daily for 6 weeks total)
- 3) **Placebo delivery** (0, 0, 0, 0 mg films daily for 6 weeks total)

Participants will be directed to take one film every 3-4 hours, in a specified order, for a total of four films consumed daily. In the event that participants miss taking a scheduled film, they will be instructed to skip the film if more than 8 hours has passed since they took their last film. They will be asked to indicate on their daily diary if a film was missed..

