10.7 Statistical tests

Statistical methods will be used to analyze the safety data to determine whether harms are occurring. Paired sample t-test (or nonparametric Wilcoxon Rank-Sum test) will be used to examine the changes in the outcome measures (CPD, CO, subjective measures, BP, HR) from the baseline.

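### The only planned tests are paired changes from baseline, so no analysis compares random delivery with steady state or placebo

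*Combined protocol and SAP*

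**What the plan says.** **Question.** Section 1.1 predicts that cessation will be "greater in subjects assigned to a random nicotine delivery regimen (as compared to those assigned to a steady state or placebo regimen").

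**Design.** Section 7.1: "This is a randomized, double-blind, placebo-controlled, parallel-group study". Section 7.4.2: "Participants will be randomized to one of three possible treatment regimens". Section 8.2 gives 15 per arm and Section 8.1 a total of 45.

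**Primary endpoints.** Section 1.2: "percent reduction in the number of cigarettes smoked and the accompanying percent reduction in exhaled carbon monoxide (CO) levels".

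**Analysis.** The whole of Section 8.3 is "Paired sample t-tests (or nonparametric Wilcoxon Rank-Sum tests) will be used to examine changes in the outcome measures", followed by a list (cigarettes per day (CPD), CO, subjective measures, blood pressure, heart rate) and the reference point, baseline. Section 10.7, under safety monitoring, says nearly the same: "Paired sample t-test (or nonparametric Wilcoxon Rank-Sum test) will be used to examine the changes in the outcome measures".

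**Entry and instructions.** Section 3.1 requires at least 10 "cigarettes/day for at least the past 12 months" and exhaled CO of at least "6 ppm at baseline visit". Section 7.2.4 tells every participant, whatever the arm, to stop smoking from the morning after Visit 3.

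**Only other hint of a model.** Section 7.4.6.5 says concomitant medications will serve as covariates. It names no model, outcome or contrast.

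**The concern.** A paired test asks whether smoking fell. The hypothesis asks whether it fell more with random delivery than with the other two regimens. Every arm starts with established smokers who are then told to quit, so a fall in CPD and CO is expected even on placebo. Whether the paired tests are run within arms or pooled, randomization, blinding and the placebo play no part in the inference.

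Followed exactly, the plan can report that participants smoked less after being told to quit, and nothing about the regimens. Any arm comparison that was reported would have been chosen outside the protocol. With two primary endpoints and two comparators, that leaves the test, contrasts, baseline, time point, error control and handling of dropouts all open.

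**Working it through.** **1. Question against test.**

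| Item | Between arms? |
|---|---|
| Hypothesis (1.1) | Yes: random vs steady state, random vs placebo |
| Design (7.1, 7.4.2) | Yes: three parallel randomized arms |
| Endpoints (1.2) | Per-person reductions; no comparison defined |
| Tests (8.3, 10.7) | No: change from baseline only |

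**2. Does any wording supply the comparison?** The rank-sum test is by name a two-independent-sample test. Here it is offered as the alternative to a paired test of change and no groups are named, so it reads as a misnamed signed-rank test. The covariate remark in 7.4.6.5 specifies nothing.

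**3. The plan's own figure.** 3 × 15 = 45 agrees with 8.1. There is no power calculation to reproduce: 8.2 expresses confidence but gives no alpha, effect size or SD.

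**4. Illustration: paired tests when the arms truly do not differ.** Assumed, because the documents give none: SD of percent change 25, 35 or 45 points, two-sided 0.05. For n = 15, the within-arm power p comes from a noncentral t with 14 df and noncentrality √15 × fall/SD.

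| SD | 20% fall | 30% | 40% | 50% | 60% |
|---|---|---|---|---|---|
| 25 | 0.821 | 0.991 | 1.000 | 1.000 | 1.000 |
| 35 | 0.540 | 0.870 | 0.984 | 0.999 | 1.000 |
| 45 | 0.361 | 0.671 | 0.892 | 0.979 | 0.998 |

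All three arms are significant with probability p³. At a 50% fall this is 1.000, 0.998 and 0.938 (for SD 45, 0.979³ = 0.938).

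Suppose benefit were read from random being significant while at least one comparator was not. The protocol states no such rule. The chance under no true difference is p(1 − p²):
- 20% fall: 0.267, 0.383 and 0.314 (for SD 45, 0.361 × (1 − 0.130) = 0.314)
- 50% fall: 0.000, 0.002 and 0.041
- 60% fall: at most 0.005

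A simulation with reduction bounded at 100% (5 to 30% assumed to quit fully, mean falls 24 to 68%) found all three arms significant in 68 to 100% of trials, and in 100% (rounded) at mean falls of 46% or more.

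**5. Error rate of a between-arm model.** Percent reduction was regressed on arm and baseline (45 − 4 = 41 df). Over 34 simulated null cases of 40,000 trials each, one contrast at 0.05 rejects in 4.8 to 5.3%. Either of two contrasts at Holm's first step (0.025) rejects in 4.4 to 4.9%.

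**6. Power and precision, 15 vs 15, assumed 0.8 SD difference.** The unadjusted t-test has noncentrality 0.8 × √(15/2) = 2.19 on 28 df. The model columns assume a correlation r between baseline and outcome.

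| Alpha | Unadjusted | Model r = 0 | r = 0.3 | r = 0.5 |
|---|---|---|---|---|
| 0.05 | 0.562 | 0.558 | 0.600 | 0.685 |
| 0.025 | 0.441 | 0.441 | 0.484 | 0.572 |
| 0.0125 | 0.334 | 0.338 | 0.378 | 0.464 |

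An unadjusted comparison reaches 80% power at about 1.06 SD (alpha 0.05) or 1.18 SD (0.025). The unadjusted 95% CI half-width is 2.048 × √(2/15) × SD = 0.748 × SD, which is 18.7, 26.2 and 33.7 points for SD 25, 35 and 45. With the model it runs from 16.0 (r = 0.5, SD 25) to 33.2 (r = 0, SD 45).

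**7. Dropout (assumed rates).** With 3 of 15 missing per arm, r = 0 to 0.3 and alpha 0.05, power is 47 to 50% on observed cases and 16 to 34% if the missing are coded as 0% reduction. With 1, 3 and 5 missing (random, steady, placebo) coded as 0% and no true effect, random vs placebo rejects in 7 to 16%.

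**The case against.** The best defence is that 8.3 is terse rather than exclusive. It does not say that only paired tests will be run; covariates cannot enter a paired t-test; and rank-sum is a two-sample name. Both suggest that arm comparisons were in mind. But neither specifies one, and the sentence that does specify a test specifies the wrong kind.

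Other points refine the correction without removing the problem:

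- The hypothesis concerns cessation, while the primary endpoints are percent reductions. Comparing arms on the stated endpoints leaves that gap, which should be declared.
- The protocol labels Visit 1 as baseline. Using the Visit 2 CO reading is a change and should be stated as one.
- No primary time point is given, so Visit 5 is a proposal. Between Visits 2 and 3 all arms smoke freely, so the argument from the quit instruction does not cover that interval. Paired tests there still compare no arms.
- After Visit 3, cigarettes are recorded only if there is a slip, so a blank diary day may mean zero or missing.
- Section 10.7 is a safety section, where within-person change is a reasonable summary. It does not fill the efficacy gap.
- All SDs, correlations and dropout rates above are assumed.

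**Conclusion.** The concern holds and must be fixed. The stated tests answer a different question from the hypothesis, and no other section supplies the missing comparison. This follows from the text and depends on none of the assumed figures. Those figures show only that, with a large common fall, significance in every arm is close to certain and uninformative. The misleading pattern of unequal significance matters mainly when the common fall is small (27 to 38% at a 20% fall, 0 to 4% at 50%).

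**What to change.** In Section 8.3, make the primary analysis a between-arm comparison of percent reduction in CPD and in exhaled CO, from the pre-randomization value to Visit 5:

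- **Baseline.** For CPD, the diary kept between Visits 1 and 2 (nominally seven days). For CO, the Visit 2 reading, taken before product is supplied, not the Visit 1 reading used for eligibility. Say that this departs from the protocol's baseline label.
- **Model.** A linear model with arm and that baseline value. Two contrasts, random vs steady state and random vs placebo, each with an estimate and 95% CI. If Visit 5 levels are modelled instead, state that the scale changes.
- **Population and missing data.** All randomized participants in their assigned arm, with one rule for those without Visit 5. An example is multiple imputation from arm, baseline, Visit 3 and Visit 4 values (not simulated here). Keep 0% reduction as a sensitivity analysis only, given step 7. A rule is needed because 3.3.2 provides replacement only before randomization, and under 3.3.1.2 those who choose to leave are not contacted again.
- **Error control.** Holm over the two contrasts is one option. State whether CO is supportive, must also succeed, or can succeed alone; the last makes four tests with a first step of 0.0125.
- **Covariates.** Pre-randomization medications only.
- **Within-arm changes.** Descriptive, naming the signed-rank test where paired change is meant, in 8.3 and 10.7.

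The sponsor should settle the CPD window, any rank-based fallback, the coding of blank diary days that staff could not verify, and how percent reduction relates to the cessation hypothesis.

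The cost is wording only, with no new data collection. The drawback is the low power and wide intervals in step 6, which the protocol should acknowledge by presenting results mainly as estimates.

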2.2 Previous Data

Support for our random delivery hypothesis is provided by both preclinical and clinical data suggesting that yoked (i.e., uncontrollable/unpredictable) delivery of drug impairs the development of cue-drug associations, retards or disrupts responding for drug or alcohol, and can even render the drug aversive. In rats, yoked delivery of ethanol retarded later acquisition of ethanol self-administration⁸ and, in our hands, a history of yoked delivery of cocaine⁹ disrupted the willingness to work for the drug on a progressive ratio schedule of reinforcement. Although fixed ratio (FR) responding appears normal in rats with a history of yoked delivery of cocaine, the averaged data occlude the fact that rats yoked to high

drug-takers actually took only about 4 infusions/hour on the FR schedule. To be effective, however, yoked delivery of drug needs not only delay acquisition in drug inexperienced rats, but must effectively rescue subjects with a strong drug habit. In accordance, Twining and Mueller (in preparation) found that yoked delivery of cocaine rescued cocaine-experienced rats by reducing drug seeking during extinction and by reducing drug-taking during subsequent FR testing. In humans, Donny et al¹⁰ reported that yoked delivery of cocaine led to an increase in mean systolic and diastolic blood pressure in response to the drug because of a lack of cue-supported tolerance. Scheduled availability of ethanol led to a marked decrease in intake of ethanol in a controlled setting.¹¹ Finally, a meta-analysis showed that pre-cessation treatment with a standard (i.e., steady state) nicotine patch doubled the odds of quitting smoking relative to subjects that received only post-cessation treatment with the nicotine patch.¹²⁻¹⁴ Rose and Behm, too, found abstinence enhanced by pre-cessation treatment with the nicotine patch.¹⁵ [name] reported that use of the nicotine patch while smoking led to a 14% reduction in expired carbon monoxide (CO), reduced satisfaction from smoking, and fewer and weaker reported urges to smoke.¹⁶ These marked effects are thought to be due, at least in part, to separation of blood nicotine levels from the act of smoking.¹⁵ Dissociation of smoking behavior and cues from nicotine is expected to be even greater with random nicotine delivery.

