- 7.2.1.10** Participants will be instructed to continue smoking their usual brand of cigarettes for the next week, to avoid using any other tobacco products, and to maintain a daily diary of cigarette use on which they will record the number of cigarettes they smoke each day.
- 7.2.1.11** Participants will be compensated for completing the study visit and procedures.

7.2.2 Pre-Cessation Phase – Visit 2 [1 week after Visit 1] (Day 0 -1/+3 days)

- 7.2.2.1** Adverse events will be documented.
- 7.2.2.2** The cigarette daily diary will be reviewed and recorded by the researcher to confirm that the participant completed their diary, that ≥ 10 cigarettes were smoked on at least 5 out of the last 7 days, and that no quit attempts have been reported. If any of these criteria have not been fulfilled, the participant will be excluded from randomization, and the End of Trial Form will be completed.
- 7.2.2.3** Use of other tobacco products in the past 7 days will be assessed. If the participant has used any other tobacco product in the past 7 days, they will be excluded from randomization, and the End of Trial Form will be completed.
- 7.2.2.4** Concomitant medications will be assessed to confirm participants have not initiated nicotine replacement therapy or cessation medication use since Visit 1. If they have initiated either of these medication categories, they will be excluded from randomization, and the End of Trial Form will be completed.
- 7.2.2.5** Participants who meet all eligibility criteria for randomization will complete the measures and study procedures indicated on the Time & Events Table for the visit.
- 7.2.2.6** Following randomization, subjects will receive their assigned study products. Research staff will explain how to use the nicotine films and provide participants with administration and dosing instructions. Participants will receive a 14-day plus 3-day supply of the assigned film regimen (68 films total). The films will be packaged and numbered so they are taken in a specific, sequential order throughout each day. Participants will be instructed to take one film every 3-4 hours each day for a total of 4 films per day.
- 7.2.2.7** Participants will be asked to return all used (opened/empty) and unused (unopened) study product pouches at their next study visit.
- 7.2.2.8** Participants will be instructed to continue smoking their usual brand of cigarettes ad libitum over the next two weeks and to avoid using any other tobacco products.

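### The nonparametric fallback for change from baseline is named as the Wilcoxon rank-sum test, an independent-samples test; the paired counterpart is the Wilcoxon signed-rank test

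*Combined protocol and SAP*

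**What the plan says.** Section 8.3 is the whole of the statistical methods text. It reads: "Paired sample t-tests (or nonparametric Wilcoxon Rank-Sum tests) will be used to examine changes in the outcome measures". The outcomes listed are cigarettes per day, CO, the subjective measures, blood pressure and heart rate, and the comparison is with baseline.

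Section 10.7 applies the same choice of tests to the safety data: "Paired sample t-test (or nonparametric Wilcoxon Rank-Sum test) will be used to examine the changes in the outcome measures".

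No other section names the signed-rank test, assigns the rank-sum test to a comparison between arms, or says when the nonparametric test replaces the t-test. Section 8.2 gives the arm size as "n=15 per treatment arm".

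**The concern.** Each change from baseline uses two measurements on one participant. The paired t-test handles this by analysing the within-person differences. The Wilcoxon rank-sum (Mann-Whitney) test pools the baseline and follow-up values, ranks them together, and computes its variance as if they came from different people. It is therefore not the nonparametric version of the test it is meant to replace.

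If it were run as named, its error rate would depend on the within-person correlation. At positive correlation it is conservative and loses power. At zero correlation it is about right. At negative correlation its false-positive rate is inflated.

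The sentence in 8.3 is the only efficacy analysis stated, and it covers cigarettes per day and CO, the measures behind both primary endpoints in section 1.2. In 10.7 the same tests are meant to show whether participants are being harmed, so a conservative test could miss a modest rise in blood pressure or heart rate. An analyst who follows the text literally runs the wrong test; one who silently corrects it departs from the written plan.

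**Working it through.** **Nothing to reproduce.** The document gives no alpha, power, effect size, SD or correlation for this analysis. The only related figures are the 45 randomized (section 8.1) and 15 per arm (section 8.2), which agree: 3 × 15 = 45. The size of the problem therefore has to be shown under assumptions.

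**Inputs**
- n = 15, one arm (section 8.2).
- Two-sided alpha 0.05: assumed.
- Within-person correlation ρ from -0.3 to 0.7: assumed. The negative value only shows the direction of the error; nothing in the document suggests it.
- CO lognormal, mean 20 ppm, CV 0.4 (range 0.3 to 0.5), rounded to 1 ppm: assumed. The 6 ppm floor, applied before any reduction, follows the entry criterion in section 3.1.
- A 14% fall in CO: section 2.2 reports this for a nicotine patch used while smoking. Carrying it over to the film is an assumption.

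Pre-quit CO is a natural example of a modest change. Section 7.2.2.8 states: "Participants will be instructed to continue smoking their usual brand of cigarettes ad libitum over the next two weeks". CO is next measured at Visit 3, Day 14.

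**Step 1: why pairing matters.** With equal SD σ at both times, the true variance of the mean difference is 2σ²(1 − ρ)/n. A test that assumes independence uses 2σ²/n. Its standard error is too large by 1/√(1 − ρ), which is 1.20, 1.41 and 1.83 at ρ = 0.3, 0.5 and 0.7. As a normal approximation, the effective critical value is 1.96/√(1 − ρ). At ρ = 0.5 this is 1.96/0.707 = 2.77, a two-sided error rate of about 0.6% in place of 5%. At ρ = 0.3 it is 2.34, or about 1.9%.

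**Step 2: false-positive rate by simulation, n = 15** (40,000 bivariate-normal samples per correlation; 20,000 for the CO model)

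| ρ | Rank-sum, normal data | Rank-sum, CO model |
|---|---|---|
| -0.3 | 7.6% | 7.5% |
| 0 | 4.5% | 4.5% |
| 0.3 | 2.0% | 2.0% |
| 0.5 | 0.8% | 0.8% |
| 0.7 | 0.1% | 0.2% |

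Over the same range the paired t-test stays at 4.7 to 5.1% and the signed-rank test at 4.3 to 4.9%. The simulated rank-sum values agree with the approximation in step 1.

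**Step 3: power for a 14% CO fall, n = 15, CV 0.4** (20,000 runs, all three tests on the same samples)

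| ρ | Paired t | Signed-rank | Rank-sum |
|---|---|---|---|
| -0.3 | 13.8% | 12.9% | 20.1% |
| 0 | 15.6% | 14.8% | 16.1% |
| 0.3 | 20.5% | 19.2% | 12.1% |
| 0.5 | 27.2% | 26.1% | 9.5% |
| 0.7 | 40.0% | 39.2% | 6.4% |

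The higher rank-sum figure at ρ = -0.3 reflects its inflated false-positive rate and is not a gain. At ρ = 0.5, CV 0.3 gives 43.4 / 41.4 / 19.4% and CV 0.5 gives 19.0 / 18.8 / 6.3%, in the same order of tests.

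**Step 4: a different model.** With normal data and a 0.5 SD shift at ρ = 0.5, signed-rank against rank-sum power is 0.41 against 0.18 at n = 15, and 0.89 against 0.68 at n = 45.

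**Step 5: all 45 pooled.** The plan does not say whether the change is tested by arm or overall, so pooling is a further assumption. Taking 30 active participants with a 14% fall and 15 placebo participants with none (section 7.4.2: "0, 0, 0, 0 mg films daily for 6 weeks total"), power at ρ = 0.5 is 34.4 / 35.2 / 14.1% for paired t / signed-rank / rank-sum (5,000 runs).

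**Step 6: large post-quit falls, n = 15.** Assume each participant has a 20% chance of being a quitter at 1 to 4 ppm. With a 50% fall in the rest, all three tests reach at least 99.8%. With a 30% fall in the rest, power at ρ = 0.5 is 96.4 / 95.9 / 89.4% (10,000 runs).

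**The case against.** The strongest reply is that this is a slip of the pen. The test stands in brackets as the alternative to a paired t-test for change from baseline, so the intent is clear and a competent analyst would probably pair the data. The paired t-test comes first, is valid, and performs about as well as signed-rank in every scenario above. Harm needs two things together: the fallback is used, and it is run as named. That stands, and it limits the weight of the point. It does not make the named test right, and with no rule for when the fallback applies, its use cannot be ruled out.

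Second, the hypothesis in section 1.1 is a comparison between arms, which no test of within-person change can settle. That also stands. The missing between-arm test is a separate matter.

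Third, the 14% example is selective: even signed-rank misses that effect most of the time, and large post-quit falls are found anyway. The loss is indeed confined mainly to modest changes, but there it is more than half the power at ρ = 0.5.

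Fourth, section 1.2 defines the primary endpoints as percent reductions, whereas the simulation tests raw ppm as 8.3 is worded, and only for CO. The figures therefore do not measure the loss on the percent endpoint. But a percent reduction is a single value per person. A signed-rank test against zero applies to it directly, and a baseline-versus-follow-up rank-sum test does not.

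A last possibility is that rank-sum was meant for change scores between arms. The sentences mention no arms, and a two-sample test would not by itself cover three.

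**Conclusion.** The concern holds. Sections 8.3 and 10.7 both name an independent-samples test as the substitute for a paired one, and nothing elsewhere corrects it. Run as named at n = 15, the false-positive rate falls from about 5% to 2.0%, 0.8% and 0.1% (normal data) at correlations of 0.3, 0.5 and 0.7. Power for a 14% CO fall drops from 19.2 / 26.1 / 39.2% with signed-rank to 12.1 / 9.5 / 6.4%.

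These sizes rest on the assumed alpha, correlation, CO distribution and the patch-derived effect. That the test is misnamed rests on none of them. The correction should be made, but it is conditional in its effect, confined to within-person change, and leaves the between-arm question untouched.

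**What to change.** In sections 8.3 and 10.7, name the Wilcoxon signed-rank test as the nonparametric alternative for within-person change from baseline. Keep the rank-sum (Mann-Whitney) test only for comparing change scores between two independent arms, if such a comparison is planned.

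The cost is one term in two sections. It needs no new data, does not alter trial conduct, and has no downside.
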